4.3 Co-enrollment Guidelines

Co-enrollment into other studies will be permitted provided no drugs prohibited on this study will be given in the other study/ies and that the required blood draws do not exceed safe limits when combined with those for this study.

5.0 STUDY TREATMENT

5.1 Beating the Blues

To minimize treatment barriers, attrition, and subject burden, the BtB treatment sessions will occur in private at [name] laboratory, the ICRC, the Infectious Diseases Research Clinic at Eskenazi Health Hospital, or a remote location selected by the patient where s/he can access a computer with internet, such as the patient's home, the patient's work, a family member's/friend's home, or a public library. The location will be chosen by the participant. Patients will be provided with ear bud headphones if they plan to use them at remote locations and do not already own a pair of headphones that they would rather use. Up to 8 sessions will be performed between the Second Entry Visit and the Week 12 Visit. The PHQ-9 questionnaire will be administered at each of the Weekly BtB Sessions. No physiologic or biologic assessments will be performed during these sessions. The participants need not be fasting for these sessions.

At each in-person BtB session, a psychology research assistant trained in the use of this intervention will first collect homework and will start the appropriate session on a computer. The patient will then work through the session alone at his/her own pace. At the end of the session, the research assistant will give the patient the printed homework assignment and will schedule the next session.

Remote BtB sessions will be scheduled, just like in-person sessions. Patients who select the remote treatment option will be given a BtB binder with printouts of all future homeworks at the time of randomization (i.e., the end of the Second Entry Visit). To begin each remote BtB session, an assistant will call the patient to instruct the patient to put last week's homework in the BtB binder, to address any technical issues, and to ensure that the patient has launched the correct BtB session for that day. The patient will then work alone through the BtB session at his/her own pace, with the assistant monitoring progress remotely on the secure BtB website set

up for this trial. To end the session, the assistant will call the patient back to address any questions and ensure that the patient has identified the correct printed homework in the BtB binder.

5.2 Prohibited Medications

- Agents with significant anti-inflammatory activity (including, but not limited to, plaquenil, infliximab, etanercept, mycophenolate mofetil, sirolimus, tacrolimus, cyclosporine, pentoxifylline, theophylline, thalidomide)
- Investigational agents
- Cytotoxic chemotherapy
- Systemic glucocorticoids (topical steroids are allowed; inhaled/nasal steroids are allowed only if the participant is not also receiving HIV protease inhibitors)
- Anabolic steroids (physiologic testosterone replacement therapy is not exclusionary)

6.0 CLINICAL AND LABORATORY EVALUATIONS

6.1 Schedule of Events

Evaluation	Screening Visit	First Entry Visit (within 15 days of Screening)	Second Entry Visit #2 (within 30 days after Screening)	Weekly BtB Sessions for the intervention group (8 in total)	Week 12 Visit (for both groups; 84-105 days after Second Entry Visit)	Week 24/Closeout Visit (for both groups; 168-189 days after Second Entry Visit)
Informed Consent	X					
Documentation of HIV Status	X					
Medical/Psychiatric History	X					
Medication/Supplement Use History	X					
Updated Psychiatric Management			X		X	X
Concomitant/Updated Medications			X		X	X
PHQ-9 Assessment	X	X	X	X	X	X
Signs & Symptoms	X		X		X	X
Diagnoses/Updated Diagnoses	X		X		X	X
Height		X				
Weight		X	X		X	X
Vital Signs	X	X	X		X	X
Brief Physical Examination	X	X	X		X	X
Urine Pregnancy Test	X	X	X		X	X
Randomization			X			
Serum chemistries/glucose, total cholesterol (non-fasting)	X					
Hematology, hemoglobin A1c	X					
HIV-1 RNA level	X		X		X	X
CD4 cell count			X		X	X
Whole blood for ECFCs and monocyte subsets		X	X		X	X
DNA sampling			X			
Beating the Blues Behavioral Intervention				X		
Questionnaires			X		X	X
FMD/NTGMD		X	X		X	X
Frozen Serum for Batched Testing of Inflammatory/Coagulation Markers, Metabolic Markers		X	X		X	X
Frozen Plasma, Serum, and Urine for Future Studies		X	X		X	X

6.2 Definitions for Schedule of Events – Special Instructions and Definitions of Evaluations

6.2.1 Documentation of HIV-1 Infection

HIV-1 infection documentation must be present in the source documentation at the Screening Visit. HIV-1 infection, documented by both: (1) any licensed rapid HIV test or HIV enzyme test kit at any time prior to study entry and (2) by at least one detectable HIV-1 antigen or at least one detectable plasma HIV-1 RNA viral load.

6.2.2 Medical/Psychiatric History

A medical/psychiatric history must be present in the source documents. Record the following on CRFs at either the Screening Visit:

- Birthdate
- Sex
- Patient's self-report of ethnicity and race
- Initial date of HIV infection documentation
- Route of HIV infection
- Most recent hepatitis B surface antigen result (including date of this value)
- Most recent hepatitis C antibody result (including date of this value)
- Diagnoses (all medical and psychiatric)

6.2.3 Medication and Psychiatric Treatment History

A medication history must be present in source documents. The following information will be recorded on the CRFs at the Screening Visit:

- Start dates of current antiretroviral treatments
- Listing of all previous antiretroviral treatments
- Start dates of current antidepressant treatments
- Any other prescription medications within 30 days of Screening
- Any vaccinations within 30 days of Screening
- Any supplements (non-prescription) used within 30 days of Screening
- Previous psychiatric cognitive behavioral therapy treatments within one year of screening

6.2.4 Diagnoses

All confirmed and probable new diagnoses made since the last visit will be recorded on the CRFs, including current status at the time of the study visit.

6.2.5 Concomitant Medications

All new and/or discontinued prescription medications (including antidepressant medications), taken since the last study visit will be recorded on CRFs with start and stop dates.

6.2.6 Clinical Assessments

6.2.5.1 Height

Height will be recorded on CRFs at the First Entry Visit

6.2.5.2 Weight

Weight will be recorded on CRFs at both Entry Visits, the Week 12 Visit, and the Week 24 Visit.

6.2.5.3 Resting Blood Pressure

Blood pressure measurements will be recorded on the CRFs at each non-BtB study visit. Blood pressure measurements should be obtained prior to the brachial artery ultrasound measurements.

Blood pressure measurements should be performed on the same arm throughout the study. The participant should first sit quietly for five minutes. With the elbow and forearm resting comfortably on a flat table, the blood pressure should then be measured. After two minutes, repeat blood pressure measurement in the same arm. After another two minutes, repeat blood pressure measurements again. Therefore, three blood pressure measurements are to be documented in the CRFs.

6.2.5.4 Resting Heart rate

Resting heart rate measurements will be recorded on the CRFs at each non-BtB study visit. Heart rate measurements should be obtained prior to the brachial artery ultrasound measurements. This may be done prior to the first blood pressure measurement. The participant should first sit quietly for five minutes prior to measurement of heart rate.

6.2.5.5 Brief Physical Examination

The following assessments will be performed at each non-BtB study visit:

- Auscultation of heart for signs of cardiac arrhythmias and valvular murmurs
- Auscultation of carotid arteries for bruits

6.2.5.6 Signs and Symptoms

All signs and symptoms must be documented in the source documentation. All signs and symptoms occurring within 30 days of Screening and/or since the last study visit, regardless of grade, must be recorded on CRFs.

6.2.5.7 Laboratories

All study visit laboratory evaluations performed as part of this study must be present in source documentation. In addition, record on CRFs all values for hemoglobin A1c, white blood cell count, hemoglobin, creatinine and estimated GFR, glucose, urine pregnancy testing, total cholesterol, CD4 cell counts, and HIV-1 RNA levels.

All laboratories will be sent to the Indiana University Health clinical laboratory for immediate processing and analysis; results will be entered on CRFs and forwarded to the Biostatistical Division for electronic storage.

Brachial ultrasound results will be entered on CRFs and sent to the Biostatistical Division. Computer labels will be generated and affixed to the appropriate specimen containers or brachial ultrasound discs and will include the specimen number, participant number, specimen date, and primary specimen type. Labels must be affixed prior to freezing the vials.

NOTE: Either a single venipuncture or a peripheral IV heparin lock may be used for drawing blood samples; this venipuncture should be performed on an extremity other than the arm used for the brachial artery measurements.

6.2.5.8 Specimen Collection, Processing, Labeling, and Storage for Specimens for Future Analysis

DNA Sample

- Collection: Collect ONE (1) 7.0-mL K3 purple-top EDTA tube, FILL COMPLETELY. Place on ice immediately. Do not allow to clot. Do not spin.
- Processing: Prepare at least 4 aliquots of 1.5-mL each in 1.5-mL purple screw cap vials from the 7.0-mL whole blood EDTA tube and freeze at -80°C and store upright.
- Labeling: Label on each aliquot the protocol-subject number, date, specimen type “DNA”.

Whole blood

- Collection:
For the measurement of ECFCs and monocyte subsets, collect TWO (2) 6.0-mL, purple-top EDTA tubes, FILL COMPLETELY. After collection of blood, keep upright at room temperature.
- Processing:
Do not spin after collection. Keep at room temperature pending transfer of these purple top EDTA tubes to [name] laboratory.
- Labeling:
Label on each EDTA tube the protocol-subject number, date and time of collection, specimen type “WB ECFC”, and tube number.

Plasma

- Collection:
 - For plasma #1, collect TWO (2) 6.0-mL, purple-top EDTA tubes, FILL COMPLETELY. After collection of blood, gently invert the tube 10 to 15 times and keep upright at room temperature until centrifugation. KEEP REFRIGERATED AT 4°C AFTER DRAW IF UNABLE TO CENTRIFUGE IMMEDIATELY.
 - For plasma #2, collect an additional ONE (1) 2.7-ml, blue-top 3.2% buffered Sodium citrate (SCI) tubes, FILL COMPLETELY (for storage). Mix gently by inverting 8 times immediately after filling. DO NOT SHAKE the tube as this will break down fibrinogen in the sample. COMPLETE PROCESSING WITHIN 1 HR OF COLLECTION.
- Processing:
 - For plasma #1 tubes, spin 3000 x g for 10 minutes at 4°C. Prepare at least 6 total aliquots containing at least 0.5-mL of plasma each and freeze at -80°C within 4 hours of collection.
 - For plasma #2 tube, spin at 1500 x g for 15 minutes at room temperature. Prepare at least 2 total aliquots containing at least 0.5-ml of plasma each and freeze at -80°C within 60 minutes of collection.

- Labeling: Label on each aliquot the protocol-participant number, date, specimen type “E-PLA” and “S-PLA”, and aliquot number as appropriate.

Serum

- Collection: Collect ONE (1) 10.0-mL red-top tube without additive at room temperature. Let blood clot 30 minutes at room temperature in vertical position.
- Processing: Spin tube for 10 minutes at 1300 x g to separate serum within 1 hour of collection. Prepare at least 6 total aliquots containing at least 0.5-mL of serum. Separated serum **MUST** be refrigerated until frozen. Freeze at -80°C as soon as possible within 8 hours of collection. **REFRIGERATE ALIQUOTS IF FREEZING CANNOT BE ACCOMPLISHED IMMEDIATELY AFTER PROCESSING.**
- Labeling: Label on each aliquot the protocol-participant number, date, specimen type “SER”, and aliquot number.

Urine

- Collection: Collect at least 5-mL of urine in a standard collection cup using clean catch technique.
- Processing: Prepare at least 4 total aliquots containing at least 0.5-mL in screw-top plastic vials and freeze at -80°C.
- Labeling: Label on each aliquot the protocol-participant number, date, and specimen type “URI”.

6.2.5.9 Brachial artery ultrasound measurements

All brachial artery ultrasound measurements must be recorded on CRFs.

Perform the assessment in the morning to avoid adrenergic stimulation after an overnight fast (approximately 8 hours).

Participants may not use tobacco-containing products or eat or drink anything other than water for 8 hours prior to the assessment and until it is completed.

Patients with a history of migraine headaches may participate in this trial but will not undergo the nitroglycerin-mediated dilation portion of the brachial artery ultrasound testing.

See section 3.6 for the ultrasound procedure.

7.0 ADVERSE EVENT MANAGEMENT

Although not an inherent risk of the study intervention or study procedures, participants for this study are eligible only if they have depression as determined through completion of the PHQ-9 questionnaire. As such, these participants may have suicidal ideation at screening or develop suicidal ideation during the course of the study. We have already put into place a protection protocol for just this event in our previous studies in HIV-uninfected depressed patients (please see Appendix at end of this protocol). If a participant reports having thoughts of being better off dead or of hurting him/herself (i.e., responds with a 1, 2, or 3 to PHQ-9 Item #9 or spontaneously reports suicidal ideation), the visit will be immediately stopped, and the research assistant will interview the participant to complete the Patient Suicidality Form (see Appendix). If the participant answers “no” to all three suicide questions or if the patient answers “yes” only to Question 3 (previous attempt) and the most recent attempt was ≥ 10 years ago, the visit will proceed as normal, and the completed Patient Suicidality Form will be given to the principal investigator.

If the participant answers “yes” to any of the three questions (for Question #3 the previous attempt must be within the past 10 years), the research assistant will immediately contact the principal investigators. [name] (a clinical psychologist) and [name] (a physician) will review the case as soon as possible, but no later than the same day, to determine the appropriate course of action (e.g., immediately contact the patient’s primary care provider, primary HIV provider, clinical social worker, or care coordinator, consult with clinicians

at Midtown Community Mental Health Center, and/or escort the patient to the Crisis Intervention Unit at Eskenazi Health). Additional authorities, including the police, may be contacted if immediate harm is of concern. Participants may be withdrawn from the study.

A direct correspondence by phone call and letter (both an email and a hard copy version), will also be sent to the potential participant's primary provider notifying him/her of the situation (see below).

If an enrolled participant reports having thoughts of being better off dead or of hurting him/herself during any telephone calls (e.g., a scheduling call or a call to the study team initiated by the participant), the exact same procedures as outlined above will immediately be initiated. Please see the Appendix for the full Suicide Management Plan.

Since it is unknown if depression therapy (or lack thereof) results in somatic adverse events in antiretroviral-treated HIV-infected patients, we will also carefully document Grade 3 or 4 level toxicities defined using the Division of AIDS Table for Grading Adult Adverse Experiences. Clinical management decisions and decisions to discontinue participants from the trial will be made by the principal investigator(s) in conjunction with the participant's primary caregiver; care plans and outcomes must be included in the source documentation. All serious adverse events (SAEs) will be documented on CRFs with unexpected SAEs forwarded to the IUPUI IRB within 10 working days of the event and the remainder to be documented on the annual continuing review.

8.0 CRITERIA FOR STUDY DISCONTINUATION

- Request by the participant to withdraw
- Request of the primary care provider if s/he believes the study is no longer in the best interest of the participant
- If the participant is found to be pregnant or begins breastfeeding during the course of this study
- If the participant has develops fever, need for systemic therapy for acute or serious illness, or hypotension after screening that precludes completion of the study visits within the allowed timeframes
- Requirement for prohibited concomitant medication(s)
- Clinical reasons believed life threatening by the physician
- Participant, as judged by the investigators, to be at risk of failing to comply with the provisions of the study protocol as to cause harm to self or interfere with the validity of the study results

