3.4 Beating the Blues Treatment Sessions and Usual Care

3.4.1 Beating the Blues

To minimize treatment barriers, attrition, and subject burden, the BtB treatment sessions will occur in private at [name] laboratory, the ICRC, the Infectious Diseases Research Clinic at Eskenazi Health Hospital, or a location selected by the patient where s/he can access a computer with internet, such as the patient's home, the patient's work, a family member's/friend's home, or a public library. The location will be chosen by the participant. To help maintain privacy, patients will be provided with ear bud headphones if they plan to complete BtB sessions at remote locations and do not already own a pair of headphones that they would rather use. We will also tell patients that, if they choose to complete BtB session where others are present, these other people (e.g., family member or friend) may realize that they are completing a treatment for depression. It will be up to each patient to decide if the available remote locations provide sufficient privacy. Up to 8 sessions will be performed between the Second Entry Visit and the Week 12 Visit. The PHQ-9 questionnaire will be administered at each of the Weekly BtB Sessions. No physiologic or biologic assessments will be performed during these sessions. The participants need not be fasting for these sessions.

At each in-person BtB session, a research assistant trained in the use of this intervention will first collect homework and will start the appropriate session on a computer. The patient will then work through the session alone at his/her own pace. At the end of the session, the research assistant will give the patient the printed homework assignment and will schedule the next session.

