3.4.2 Usual Care

This arm was modeled after the IMPACT trial's control group (48). Patients randomized to the Usual Care group will be informed of their depression diagnosis and will be encouraged to follow-up with their primary care or HIV provider. There will be no formal interaction with the participants between the Second Entry Visit and the Week 12 Visit. However, the participants will be encouraged to contact the study team for any changes in their condition.

Our team will also send their primary provider a letter indicating that their patient has a depressive disorder and was randomized to usual care and will include a list of local mental health services. Although feedback to patients and providers could result in treatment that would not have occurred naturally, studies have shown that informational support alone is unlikely to improve depression outcomes (125). In our pilot study which used this control group, only 14% of Usual Care patients had >50% reduction in symptoms versus 43% of *Beating the Blues* patients. There will be no restrictions on the care that can be received, although we will assess changes in care during the trial.

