3.5 Week 12 and Week 24 Visits

The participant will come to the ICRC for both of these visits. The Week 12 visit will be scheduled between 84 and 105 days after the Second Entry Visit. The Week 24 Visit will be scheduled between 168 and 189 days after the Second Entry Visit. **The study participant must be fasting for these visits.**

During these visits, updated psychiatric management (such as new medical or behavioral therapies initiated since the Second Entry Visit) and medications will be reviewed. The PHQ-9, SCL-20, International Physical Activity, Morisky, Tobacco Use, General Anxiety Disorder-7, Buss-Perry Aggression, PANAS (Positive Affect subscale of the Positive and Negative Affect Schedule), and Pittsburgh Sleep Quality Index questionnaires will be administered. Vital signs will be measured and a brief physical exam will be performed prior to performing the FMD procedure and obtaining blood for the circulating markers of interest. A urine pregnancy test will be repeated for women of reproductive potential. Urine will also be obtained for archiving.

Participants who continue to exhibit elevated depressive symptoms (PHQ-9 \geq 10) at the final study visit will be urged to follow-up with their primary HIV provider and/or clinical social worker regarding their depression. In addition, the study team will notify the primary HIV provider that his/her patient has completed participation in our trial and still has clinically elevated depressive symptoms. A list of local mental health service providers and clinics will be given to the patients' primary HIV providers or social workers.

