3.6 Brachial artery reactivity indices

FMD and NTGMD will be measured according to established guidelines (126) at both Entry Visits, the Week 12 Visit, and the Week 24 Visit. These measurements will be performed at the ICRC.

Brachial reactivity measurements have considerable day-to-day variability. Variables that will transiently affect vasomotor function include environmental conditions, tobacco and alcohol use, diet, and medications (127). Therefore, it is desirable to control these factors in order to obtain results that more accurately reflect the underlying condition being studied. Therefore, the room temperature will be controlled at 68-71°F. The participant will rest supine for 10 minutes prior to imaging. Participants will be told to not use tobacco-containing products or eat or drink anything other than water for 8 hours prior to the study. Female participants will first have urine pregnancy testing performed prior to the ultrasound tests; if the participant is found to be pregnant, the participant's participation will end.

A 10 mHz linear array vascular probe for B-mode imaging will be used to visualize the brachial artery. Data will be stored on a compact disc for backup and also on the IU server with password protection. ECG leads will be placed on the participant's chest and automatic blood pressure cuff to left upper arm, set at q.15 minutes. A small forearm cuff is placed on the widest part of the participant's proximal right forearm

(approximately 1-2 cm distal to the antecubital fossa). The brachial artery will then be located with the image optimized for best resolution of all three layers of the anterior and posterior walls (with special emphasis on identifying the media-adventitia interface). Three consecutive cardiac cycles of B-mode images of the brachial artery to the disks will be acquired and stored.

After this baseline evaluation, the measurement of endothelium-dependent vasodilation, or FMD, due to increased blood flow will begin. The forearm pressure cuff will be inflated to 250 mmHg for 5 minutes. At that time, imaging will be switched to B-mode. At 60 and 90 seconds after cuff deflation, three consecutive cardiac cycles of B-mode images of the brachial artery to the disc will be acquired and stored. The greater of the two diameters measured at these time points will be used for FMD analysis.

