4.2 Exclusion Criteria

4.2.1 Inability to complete written, informed consent.

4.2.2 Incarceration at the time of any study visit.

4.2.3 Active suicidality, as determined by the patient's HIV provider or social worker following a positive response (1, 2, or 3) to PHQ-9 Item #9 and a positive response (yes) to one or more of the three questions (for Question #3, the previous attempt must be within the past 10 years) on the Patient Suicidality Form (see Appendix).

4.2.4 Diagnosed vascular disease (documented history of angina pectoris, coronary disease, peripheral vascular disease, cerebrovascular disease, aortic aneurysm, or otherwise known atherosclerotic disease).

4.2.5 History of congestive heart failure, even if currently compensated.

4.2.6 Diagnosed disease or process, besides HIV infection, associated with increased systemic inflammation (including, but not limited to, systemic lupus erythematosus, inflammatory bowel diseases, other collagen vascular diseases).

Note: Hepatitis B or C co-infections are NOT exclusionary

4.2.7 Known or suspected malignancy requiring systemic treatment within 180 days of screening.

NOTE: Localized treatment for skin cancers is not exclusionary.

4.2.8 History of Raynaud's phenomenon.

4.2.9 History of cardiac arrhythmias or cardiomyopathy.

4.2.10 Uncontrolled hyperthyroidism or hypothyroidism, defined as TSH values outside of the local reference range on most recent clinical assessment.

4.2.11 History of carotid bruits.

4.2.12 Systolic blood pressure > 160 mmHg or diastolic blood pressure > 110 mmHg at screening.

4.2.13 Screening estimated glomerular filtration rate (eGFR) < 50 mL/min/1.73m² (calculated from the 2009 CKD-EPI equation) using a serum creatinine level measured at screening.

4.2.14 Screening glucose ≥ 140 mg/dL or hemoglobin A1c > 8.0%.

4.2.15 Screening total cholesterol > 240 mg/dL.

4.2.16 Therapy for serious medical illnesses within 14 days prior to screening.

Note: Therapy for serious medical illnesses that overlaps with a main study visit will result in postponement of that study visit until the course of therapy is completed; postponement outside of the allowed study visit timeframe will result in study discontinuation.

- 4.2.17 Pregnancy or breastfeeding during the course of the study.
- 4.2.18 Receipt of investigational agents, cytotoxic chemotherapy, systemic glucocorticoids (of any dose), or anabolic steroids at screening.

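### Section 8.0 and the note to 4.2.16 take some still-measurable participants off study, and nothing in the plan keeps their Week 12 and Week 24 outcomes for the ITT analysis.

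*Combined protocol and SAP*

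**What the plan says.** Section 8.0 is headed as criteria for discontinuing the study and does not separate stopping BtB from leaving the trial. Its criteria include the participant's own withdrawal, a primary care provider's request, need for a prohibited medication, acute or serious illness that prevents visits within their windows, and a participant whom the investigators consider "at risk of failing to comply with the provisions of the study protocol as to cause harm to self or interfere with the validity" (that is, of the results).

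The note to exclusion criterion 4.2.16 first postpones a visit that overlaps with therapy for a serious illness, then adds that "postponement outside of the allowed study visit timeframe will result in study discontinuation". Section 3.5 sets the windows: "The Week 12 visit will be scheduled between 84 and 105 days after the Second Entry Visit" and "The Week 24 Visit will be scheduled between 168 and 189 days after the Second Entry Visit". For pregnancy, Section 3.6 says that "if the participant is found to be pregnant, the participant's participation will end". Section 7.0 (repeated in 10.3.2.5) and the Appendix allow withdrawal from the trial after a suicidality review.

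On the analysis side, Section 9.5 defines the ITT set as all eligible randomised patients, whatever their adherence to the planned treatment. Section 9.10 runs the primary ANCOVA of Week 12 FMD on that set. Section 9.14 provides multiple imputation, with sensitivity analyses if differential missingness is seen. Section 9.7 provides a flow chart with frequencies of completion and discontinuation, and a listing of those discontinued from BtB. No passage says whether someone discontinued under these rules is still assessed at Week 12 or Week 24.

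**The concern.** An ITT analysis needs outcomes on everyone randomised, as far as they can be had. Some Section 8.0 criteria leave nothing to collect, such as withdrawal of consent. Others can leave a person willing and able to attend. If the plan is followed as written, that person's Week 12 FMD is not taken and has to be imputed.

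The 4.2.16 note can cost two time points. A Week 12 visit pushed past day 105 ends participation, so Week 24 is lost as well, although its window has not yet opened.

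At stake is some precision and, if those removed differ from those who stay in ways the imputation model does not capture, the size of the estimated effect. The sensitivity analyses in 9.14 can probe that but cannot recover measurements that were obtainable.

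**Working it through.** **1. The plan's own figure.** Inputs from 9.3, 9.10 and the pilot table in 2.3.5: difference 1.7 FMD points, d = 0.61, two-sided alpha 0.05, power 0.80. The implied SD is 1.7/0.61 = 2.79. The two-sample t-test solution is 43.17 per arm, which rounds up to 44, or 88 in total; 88/(1 − 0.20) = 110. The stated sample size reproduces, so this is not a sample-size error. The plan allows for 110 − 88 = 22 losses.

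**2. Precision.** Power of the two-sample t-test at d = 0.61, if those kept respond like the others:

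| Planned losses kept | Analysed | Power |
|---|---|---|
| 0 | 88 | 80.8% |
| 5 | 93 | 82.9% |
| 11 | 99 | 85.2% |
| 22 | 110 | 88.7% |

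**3. Windows.** Week 12 closes at day 105 and Week 24 opens at day 168: 168 − 105 = 63 days. A participant too late for Week 12 may well be assessable nine weeks later.

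**4. Bias (illustration; none of these inputs is in the documents).** Suppose k_B BtB and k_U Usual Care participants of 55 per arm are discontinued before Week 12. Let s_B and s_U be the average amounts by which their true Week 12 FMD falls short of the imputed values. Then

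error in the difference = (k_B × s_B − k_U × s_U)/55.

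Take imputation from arm and baseline FMD, no benefit in discontinued BtB participants (s_B = 1.7) and no Usual Care losses (k_U = 0). The error is k_B/55 × 1.7:

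| k_B | Overstatement (points) | Share of 1.7 |
|---|---|---|
| 2 | 0.06 | 4% |
| 5 | 0.15 | 9% |
| 8 | 0.25 | 15% |
| 11 | 0.34 | 20% |

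Changing the assumptions changes the answer:
- If discontinued BtB participants benefited like the rest (s_B = 0), the error is 0.
- With k_B = k_U = 5 and equal shortfalls, (5s − 5s)/55 = 0.
- With k_B = 0, k_U = 5 and s_U = 1.7, the error is −0.15: the effect is understated.

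A simulation under the one-sided assumptions (55 per arm, residual SD 2.79, baseline correlation 0.5 assumed, 20 imputations, 2,000 runs) gave 0.16 at k_B = 5. It confirms the arithmetic, not the likelihood of the scenario.

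**The case against.** **A reader might infer that Section 8.0 contradicts the ITT definition.** It does not. The ITT wording concerns adherence to the planned treatment, which means BtB sessions. Missing sessions is not a Section 8.0 criterion, and 9.11 explores FMD over 0 to 8 sessions, so non-attenders are expected to be followed. The compliance criterion is narrower: it needs a risk of self-harm or of invalid results. What remains is an omission covering people formally discontinued.

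**A reader might also infer that BtB will lose more people.** In BtB, "The PHQ-9 questionnaire will be administered at each of the Weekly BtB Sessions"; in Usual Care, "There will be no formal interaction with the participants between the Second Entry Visit and the Week 12 Visit". Providers, who may request discontinuation, are told the allocation (3.4, Second Entry Visit). But missed sessions are not grounds for removal. The Appendix expects suicidal ideation to be rare and reports none among enrolled participants in two prior trials. Usual Care participants may also contact the team, and their providers may also request discontinuation. Differential loss is possible but not shown.

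**Some of these values may be hard to interpret.** The prohibited drugs in 5.2 include anti-inflammatory agents and systemic glucocorticoids, in a trial of FMD and inflammatory markers, and 3.6 names medications among the factors that transiently affect vasomotor function. This stands as a reason to flag such values and test their influence, but not to leave them uncollected.

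**Existing provisions help.** The plan has a 20% attrition allowance, payment at each visit, a 21-day window before 4.2.16 applies, a disposition flow chart and multiple imputation. The imputation model is not specified and could draw on PHQ-9 and SCL-20. These limit the harm. None of them settles whether a discontinued participant is measured.

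**Conclusion.** The point holds as a cheap improvement. As written, the plan gives up primary-outcome data that could be obtained from some participants, and a missed Week 12 window also forfeits Week 24. The precision at stake is modest: about two percentage points of power for five participants kept, assuming they respond like the others.

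Neither the number affected nor the direction of bias can be derived from the documents. The 0.15 points at five BtB discontinuations rests on no benefit in those five, no Usual Care losses, and an arm-and-baseline imputation model that 9.14 does not state. The table in step 4 should not be read as a bound: losses in Usual Care could cancel or reverse the error, and BtB participants who did worse than no benefit would exceed it. It does not support a claim that the trial will overstate the BtB effect.

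**What to change.** Leave the clinical criteria unchanged.

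1. In Section 8.0 and the note to 4.2.16, separate stopping the intervention from leaving the study. State that discontinued participants who have not withdrawn consent and can safely be assessed continue the scheduled Week 12 and Week 24 assessments and are included in the ITT analysis. Reconcile 3.6, Section 7.0, its repeat in 10.3.2.5, and the Appendix with this wording; which assessments are suitable in those cases is for the sponsor to decide.
2. Record actual visit dates and any prohibited medication. State in advance how out-of-window values are assigned to Week 12 or Week 24. Add to 9.14 a sensitivity analysis that excludes out-of-window and post-medication values.
3. Extend the 9.7 flow chart and listing to show study discontinuation by arm, reason and timing (before or after Week 12).

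The cost is protocol and SAP wording and some follow-up effort, with no added participants. Some values will be noisier. The estimated ITT difference may also be smaller: in the simulation above at k_B = 5, power was 81% with observed values against 87% with imputed ones, because under those assumptions imputation overstates the effect.
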